6. STUDY PARAMETERS/ENDPOINTS

6.1. Main study parameter/endpoint

Co-primary study endpoints:

1. Days alive out of hospital (superiority endpoint), within 14 days after study enrolment
2. Days on Therapy (DOT) with antibiotics (superiority endpoint), within 14 days after study enrolment
3. Adverse outcome (non-inferiority safety endpoint)
 - For initially non-admitted patients: any admission or death within 30 days after study enrolment
 - For initially hospitalised patients: i) any readmission, ii) ICU admission \geq 24 hours after hospitalisation, or iii) death within 30 days after study enrolment

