- It needs to be ensured that the non-inferiority endpoint is not positively impacted by direct effects of the intervention such as decisions to initiate or withhold antibiotic treatment or early discharge from the ER or hospital. E.g. if we would include hospitalisation days in the non-inferiority endpoint, we run the risk of 'compensating' the putative adverse effects.
- **Hierarchical nested design:** Superiority primary endpoints are tested first. Only if superiority to at least one of the two superiority endpoints is confirmed, is the non-inferiority safety endpoint taken into consideration [22]
- Because of the non-blinded nature of the study, outcomes should be defined objectively, so e.g. we cannot use cause-specific re-admission or cause-specific death.
- Reassessment when other microbiological results are available. Discrepant results should be handled by the treating physician based on best practice
- Different time windows have been chosen because i) impact of rapid syndromic testing on hospitalisation / antibiotics is immediate. ii) Shorter follow-up increases power for difference of 1 day. iii) Adverse outcomes may reflect late sequelae.

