12. SAFETY REPORTING

12.1. Adverse events

Definitions

Adverse Event (AE)

For this study, an adverse event is defined as any untoward medical occurrence, inappropriate patient management decision, unintended disease or injury, or untoward clinical signs in patients, users, or other persons, with any connection to study related activities, whether or not related to the IVD medical device.

Adverse device effect (ADE)

An adverse event related to the use of the BioFire®.

Serious Adverse Event (SAE)

All SAEs, regardless of relationship to the study device or procedure will be documented in the source. It is the Investigator's responsibility to determine the "seriousness" of an AE using the protocol defined terms, listed below. A SAE is an AE that results in one or more of the following for this study:

- Resulted in death: An AE that resulted in the patient's death.
- Life-threatening illness or injury: The patient was at imminent risk of dying at the time of the adverse event.
- Permanent impairment: An AE that resulted in permanent impairment of a body function, including chronic diseases or permanent damage to a body structure.
- Required in-patient or prolonged hospitalisation.
- Resulted in medical or surgical intervention to prevent life threatening illness or injury or permanent impairment to a body structure or body function.
- Led to fetal distress, fetal death or congenital abnormality or birth defects, including physical or mental impairment.

Notes:

1. Hospitalisation on Day-1 should not be reported as an AE or SAE if this is a direct consequence of the initial referral to the hospital.
2. SAEs resulting in death should be reported using the primary cause of death as the event term. The only exception is "Sudden Death" when the cause is unknown.
3. Planned hospitalisation for a pre-existing condition is not considered a SAE.

Serious adverse device effect (SADE)

Adverse device effect that has resulted in any of the consequences characteristic of a serious adverse event.

Categories of adverse events

ADVERSE EVENTS	Non-device-related	Device-related
		Applies to: - Inaccurate test result leads to indirect harm to the patient - Device causes direct harm to user or another person
Non-serious	Adverse event	Adverse device effect
Serious	Serious adverse event	Serious adverse device effect

SEVERITY OF ADVERSE EVENTS

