13. STATISTICAL CONSIDERATIONS

13.1. Sample size calculation

Co-primary endpoints used in the study:

1. Days on antibiotic treatment within 14 days (superiority endpoint)
2. Days alive out of the hospital within 14 days (superiority endpoint)
3. Adverse outcome within 30 days (non-inferiority safety endpoint)

Required sample sizes are presented for endpoint 2 and 3. Endpoint 1 is non-limiting due to having an expected smaller standard deviation compared to endpoint 2 and having the same clinically relevant effect size.

The intervention is considered successful if superiority is demonstrated for either or both endpoints 1 and 2 AND non-inferiority is demonstrated for endpoint 3. We use a hierarchical nested design: superiority primary endpoints are tested first. Only if superiority to at least one of the two superiority endpoints is confirmed, the non-inferiority safety endpoint is taken into consideration. To maintain an overall alpha < 0.05, the two superiority endpoints will be tested using a two-sided alpha of 0.025, while the non-inferiority endpoint will be tested using a one-sided alpha of 0.05. The minimal power for the superiority endpoints is set to 0.9 and for the non-inferiority endpoint to 0.95. This is to maintain overall power of the trial, given the hierarchical testing. For 'Adverse outcome' we considered different non-inferiority margins. For 'Days on antibiotic treatment' and 'Days alive out of the hospital' we defined 1 day as a clinically relevant effect size.

The distribution of endpoint 2 is yet unknown for the ARI population. We supported our sample size calculation using data of patients presenting with CAP to Dutch ERs and hospitalised to a non-ICU ward (ClinicalTrials.gov: NCT02604628). The standard deviation (SD) of 'Days alive out of the hospital within 14 days' in this population was 4 days. The theoretical maximum SD with a 14 days follow-up period is 7 (which would be the case if 50% had zero days and 50% had 14 days alive out of the hospital). However, we expect that in the target population the variability for this endpoint will be less than in the CAP population. We varied the SD to assess the impact on

the sample size. We used a standard correction factor of 1.15 for non-normality of the data. (Table 1) Hence for the superiority endpoints a sample size of 457 per arm would be adequate.

Table 1: Sample sizes for Days alive out of the hospital using different assumptions

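### Admissions already scheduled before enrolment count as adverse outcomes in the non-inferiority endpoint, adding events that the test cannot affect

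*Combined protocol and SAP*

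**What the plan says.** Section 6.1 makes adverse outcome the third co-primary endpoint, tested for non-inferiority. It has two branches:

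- For patients not admitted at first: "any admission or death within 30 days after study enrolment".
- "For initially hospitalised patients: i) any readmission", or late ICU admission, or death, over the same 30 days.

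The summary in section 2 gives the same definition. Neither these sections nor section 13 separates planned from unplanned admissions.

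Section 7.1 gives the reason for all-cause components. The trial is unblinded, so "outcomes should be defined objectively, so e.g. we cannot use cause-specific re-admission or cause-specific death". It does not discuss admissions arranged beforehand.

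The notes to section 12.1, which concern safety reporting only, state: "Planned hospitalisation for a pre-existing condition is not considered a SAE".

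Section 13.1 requires non-inferiority on this endpoint, as well as superiority on at least one other, before the intervention is called successful. It assumes 10% incidence in both arms and a 5-point margin, which gives 780 per arm. The total target is 1600. It gives no source for the 10% and does not say whether planned admissions are part of it.

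**The concern.** A patient seen for a respiratory infection may already have a date for an elective procedure within the next 30 days. As section 6.1 is worded, that admission is a failure on the safety endpoint, in either arm, whatever the rapid test shows. Section 13.2 names older patients and those with chronic pulmonary, cardiovascular or metabolic disease among the risk groups of interest, so such cases are plausible. The documents give no rate.

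Randomisation balances these events in expectation, so they do not favour one arm. They do raise the incidence, and with it the variance of the risk difference. They also hide a little of any true excess, because a patient who fails through a planned admission cannot fail again. In a non-inferiority comparison that dilution works in the permissive direction.

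The objectivity argument in section 7.1 is about judging the cause of an event after allocation is known. Whether an admission was on the calendar before randomisation is a dated fact that allocation cannot change, so the argument does not reach it.

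**Working it through.** **Inputs.** Section 13.1 supplies the margin (0.05), equal incidence in both arms (0.10, or 0.05 in the alternative row), and the error rates: "the non-inferiority endpoint will be tested using a one-sided alpha of 0.05", and "The minimal power for the superiority endpoints is set to 0.9 and for the non-inferiority endpoint to 0.95". The planned-admission rate q is an assumption, varied below.

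**The plan's own figure.** With unpooled variance and no true difference, n per arm = (1.645 + 1.645)² × 2p(1−p) / 0.05².

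- p = 0.10: 10.82 × 0.18 / 0.0025, rounded up, gives 780.
- p = 0.05: 10.82 × 0.095 / 0.0025, rounded up, gives 412.

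Both match the plan. Inverting the formula, power = Φ(0.05/SE − 1.645) with SE = √(2p(1−p)/n). At p = 0.10 and n = 780, SE = 0.01519 and power is 95.0%.

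**Case A: planned admissions come on top of the 10%.** If they are independent of other events, p = 0.10 + 0.90q.

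| Assumed q | p | Power, 780 per arm | Power, 800 per arm | n per arm for 95% |
|---|---|---|---|---|
| 0.5% | 10.45% | 94.3% | 94.8% | 811 |
| 1% | 10.9% | 93.6% | 94.1% | 841 |
| 2% | 11.8% | 92.2% | 92.7% | 902 |
| 3% | 12.7% | 90.7% | 91.3% | 960 |

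With all 800 per arm evaluable, power passes below 95% once total incidence exceeds about 10.3%.

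**Case B: planned admissions are already inside the 10%.** Power as designed stays at 95.0%. Excluding them lowers p and raises power at 780 per arm:

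- 1 point removed, p = 9%: 96.5%.
- 2 points removed, p = 8%: 97.7%.

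**Low-incidence case.** If the true incidence is 5%, adding 2 points gives 7%, and power at 780 per arm is still 98.7%.

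**Dilution at the margin.** Take a true excess of exactly 5 points (10% against 15%) and q = 2% in both arms.

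- Control: 0.10 + 0.02 × 0.90 = 0.118.
- Intervention: 0.15 + 0.02 × 0.85 = 0.167.
- Observed excess: 0.049.
- SE = √((0.118 × 0.882 + 0.167 × 0.833)/780) = 0.01766.
- Probability of declaring non-inferiority: Φ((0.05 − 0.049)/0.01766 − 1.645) = 5.6%, against 5.0% with no planned admissions.

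At q = 1% the corresponding figure is 5.3%.

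**The case against.** The strongest reply is that the 10% is the assumed incidence of the endpoint as defined, so planned admissions belong inside it and no stated power is lost. That is a natural reading and it cannot be ruled out. A reader might infer from the wording of section 6.1 that the stated 95% power is eroded. The documents do not support that: it needs case A, and a rate that they do not give. Section 13.5 also allows for the sample size assumptions to be checked after the first season, although it sets no rule.

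Secondly, all-cause counting is deliberate and reasoned. An elective admission that is postponed, brought forward or changed in purpose after an acute infection would have to be classified by staff who know the allocation. This stands against a loose rule of counting unplanned admissions only. It does not stand against an exclusion fixed by a baseline record, with every unclear case counted.

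Thirdly, a reader might see a contradiction between sections 6.1 and 12.1. There is none. SAE rules serve event reporting, while the endpoint serves a randomised comparison. The contrast shows only that the plan recognises planned hospitalisation as a separate kind of event. Nor does it mean that the information is already captured for every admission: under section 12.2, events are recorded in the source, but only those judged related are reported to the sponsor.

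Finally, section 13.2 says that a statistical analysis plan will follow, and section 3 says that it is shared with the paediatric study. A working definition may be placed there.

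**Conclusion.** The point holds as a small and inexpensive improvement. As worded, section 6.1 counts pre-scheduled admissions and readmissions, and the reason given for all-cause counting does not require this.

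The certain part is directional: these events add variance and slightly dilute a true excess. At an assumed 2% rate the dilution is 0.1 point, and false non-inferiority at the margin rises by about 0.6 percentage points.

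The effect on power is conditional. It ranges from a loss of about 1.4 to 2.8 points at 780 per arm (assumed 1-2% on top of 10%) to no loss at all (already inside the 10%). In both cases exclusion brings power to the stated 95% or above, provided that the remaining incidence is no higher than 10%. None of this shows that the trial is underpowered or that all-cause counting in general is wrong.

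**What to change.** - In section 6.1, exclude only an admission or readmission that was recorded at baseline, before randomisation, as already scheduled for a named procedure or reason. Count every other admission of any cause, including one whose purpose changed or whose earlier scheduling was not recorded. The rule then leaves no unblinded judgement.
- Keep the analysis that counts all admissions as a sensitivity analysis.
- In section 13.1, state whether the 10% includes planned admissions and where the figure comes from.

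The cost is one extra baseline field in the eCRF and a slightly less simple endpoint definition. The field needs to be in place before patients are randomised: scheduling status collected afterwards would be labelled with the allocation known, which is the problem that section 7.1 sets out to avoid.

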6.2. Secondary endpoints

- Direct costs and indirect costs within 30 days after enrolment.
- Change in quality of life as determined by EQ-5D-5L on day 1, 14 and 30 after enrolment. Extended follow up (up to 6 months) in a subgroup of patients that were initially hospitalised.
- Microbiological results obtained as standard of care and with the diagnostic intervention
- Empirical antibiotics, antibiotic type switches, de-escalation based on antimicrobial agent categories [21]. Prescription of antivirals during the main study.
- Detection of antimicrobial resistance (carriage or infection) related to the diagnostic intervention results compared to standard of care and impact on antimicrobial stewardship guidelines and prevention of hospital acquired infections.
- Decisions regarding isolation measures related to test result.

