5. OBJECTIVES

5.1. Co-primary objective:

To assess the impact of rapid syndromic testing in patients presenting with CA-ARTI in the ER on:

1. Days in hospital within 14 days after study enrolment
2. Days with antibiotic therapy within 14 days after study enrolment
3. Occurrence of adverse outcome within 30 days after study enrolment

5.2. Secondary objectives:

1. To assess the impact of rapid syndromic testing on healthcare utilization.
2. To assess the impact of rapid syndromic testing on quality of life.
3. To quantify the additional diagnostic yield and sensitivity of rapid syndromic testing because of targets not included in standard of care testing.
4. To quantify the impact of rapid syndromic testing on antimicrobial de-escalation and the choice of antibiotics and prescription of antivirals.
5. To quantify the impact of rapid syndromic testing on detection of antibiotic resistance.
6. To assess the impact of rapid syndromic diagnostic testing on patient bed management and/or isolation measures.

5.3. Exploratory objectives:

- Collect comprehensive data on clinical status and laboratory results for development and validation of clinical algorithms.
- To describe the current routine diagnostic and antimicrobial stewardship policy in Europe and identify good practices
- To estimate the impact of rapid syndromic testing on primary and secondary endpoints for subcategories of hospitals with similar routine diagnostic and antimicrobial stewardship programs.

- To explore clinician views and experiences of the use of rapid syndromic diagnostic testing when patients present to emergency departments (qualitative process evaluation by social sciences).

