10.2. Randomisation and blinding

Due to the nature of the intervention, blinding is not possible. After all eligibility criteria have been verified and informed consent has been obtained, randomisation will be performed using the built-in randomisation module of the eCRF system. Allocation will be concealed until the moment of randomisation. To this end, block randomisation will be used with variable blocks of size 2, 4 and 6. Randomisation will be stratified by centre. After the decision to randomise the patient is made, patients will not be excluded from the trial. If the allocated intervention is not applied for any reason, this will be recorded and follow-up for the participant will be completed.

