10.4. Clinical data set

Inclusion. Check for inclusion and exclusion criteria and randomisation. Informed Consent Form.**Baseline registration and investigations.**

Signs and symptoms at ER and management plan

Participant background

Vaccination

Co-morbidities and chronic medication

Standard of care haematology and biochemistry

EQ-5D-5L questionnaire

Management: Clinical decision after randomisation and initial results

Investigations: respiratory, urine, faeces, blood, SARS-CoV-2, radiology (only when standard of care)

Day 14: symptoms, EQ-5D-5L questionnaire

Day 30: symptoms, EQ-5D-5L questionnaire

Month 3 (if applicable): symptoms, EQ-5D-5L questionnaire

Month 6 (if applicable): symptoms, EQ-5D-5L questionnaire

Outcomes and safety:

Antibiotic treatment

Antiviral and antifungal agents

Hospital course

Device deficiency

(Severe) Adverse Event

Deviation

End of study

Table 1. Visit Schedule

Procedures	Screening	Enrollment	Hospitalization Period ^e	Face to face, on line questionnaire or phone call		Phone call Extended FU	Phone call Extended FU
	Pre- study procedures	Day 1	> Day 1	Day 14	Day 30	3 months ^f	6 months ^f
	Day 1						
Informed consent	X						
Eligibility criteria	X						
Demographics ^a	X						
Baseline assessment ^b	X						
Vaccination status	X						
Comorbidities and chronic medications	X						
Hospital course ^c		X	X ^e				
Microbiological testing ^d		X	X				
Concomitant therapy review	X	X	X ^e	X	X	X ^f	X ^f
Symptoms review and hospitalizations	X	X	X ^e	X	X	X ^f	X ^f
Quality of life questionnaire EQ5D		X		X	X	X ^f	X ^f

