10.5. Baseline and follow-up data for health-economic analysis

Follow up Assessments: Timepoints: Day 1, Day 14 and Day 30. · 3 months and 6 months for patients included in Extended Follow up

Individual patient data will be clustered in four main categories:

patient status prior to consultation (including quality of life assessment), diagnostics (including microbiological diagnostic tests and thoracic imaging), medicines (antibiotics and any other prescribed medication at the ER/admission including several parameters, antibiotic prescription in the previous 14 days) and patient follow-up (quality of life, adherence to treatment, duration of complaints).

Quality of life- (see eCRF completion guidelines on guidance) The EQ-5D (<https://euroqol.org>) contains 5-dimensions ("5D") related to everyday living: mobility, self-care, usual activities, pain/discomfort, and anxiety/depression. Patients rate the problems they have with each of these dimensions on a 5-level scale ("5-L") from 1 (no problems) to 5 (extreme problems). The second part of the EQ-5D-5L asks patients to grade their current global health status from 0 (worst health you can imagine) to 100 (best health you can image). The questionnaire form takes ± 5-10 min to administer. It needs to be completed by patient or person who has known the patient for > 5 years. (Order of preference: caregiver > spouse > children 18+ > sibling > other acquaintance). For patient questionnaires, patients will receive a link per email to complete the questionnaires online, which will directly be incorporated into the eCRF and be regarded as source data once digitally completed by the patients. If this is not possible or if patients are seen face to face, questionnaires will be completed per paper (source data) and entered in the eCRF by study staff at the site. In this case paper versions will be stored as source data. The third option to have the questionnaires completed is the use of the Interviewer version in which the study staff will interview the patient and complete the data on the paper form (source data) after which data will be entered in the eCRF.

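### No rule places the Day-1 EQ-5D-5L before randomisation, so the only baseline for quality-of-life change can be recorded after the arm is known

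*Combined protocol and SAP*

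**What the plan says.** Secondary objective 2 (section 5.2) is "To assess the impact of rapid syndromic testing on quality of life", and section 6.2 turns it into "Change in quality of life as determined by EQ-5D-5L on day 1, 14 and 30 after enrolment". Initially hospitalised patients in the extension study are followed to 6 months, and no other starting value is collected for them.

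Table 1 in section 10.4 has two Day-1 columns, Screening and Enrollment. Consent, eligibility, demographics, baseline assessment, vaccination status and "Comorbidities and chronic medications" are marked under Screening only. The row "Quality of life questionnaire EQ5D" is empty under Screening and first marked under Enrollment, as are hospital course and microbiological testing. The list in 10.4 puts EQ-5D-5L under its baseline heading, ahead of the management item.

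Section 10.5 covers Day 1, Day 14 and Day 30. It places quality of life in the data category "patient status prior to consultation (including quality of life assessment" and says that "patients will receive a link per email to complete the questionnaires online, which will directly be incorporated into the eCRF". Paper is the alternative when the link is not possible or the patient is seen face to face, and an interviewer version is the third option. Section 10.3 fixes the first collection only as the day of enrolment. On masking, section 10.2 states: "Due to the nature of the intervention, blinding is not possible".

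**The concern.** A baseline should be fixed before allocation can influence it. EQ-5D-5L asks about current health and includes an anxiety/depression item and a 0-100 self-rating, so the answer depends on when it is given. A patient who already knows the arm, the test result, or whether they are going home may answer differently. If that reaction differs between arms, the Day-1 means differ because of the allocation, and the change score removes part of a real effect or creates a false one. Quality of life is also collected for the health-economic analysis. A baseline recorded too late cannot be recovered afterwards, and without a recorded completion time nobody can tell which forms are affected.

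**Working it through.** The plan has no figure of its own to reproduce here. Section 13.1 sizes the trial on the co-primary endpoints, and section 13 gives no EQ-5D standard deviation, effect size or test. The check is mainly a reading of the text.

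**Step 1: is an order fixed anywhere?**
- Table 1: the form is in the Enrollment column, not the Screening column. The two columns are used selectively: concomitant therapy and symptoms review are marked in both, EQ-5D in one. The Day-1 mark carries no footnote letter.
- Section 10.3: a calendar day, with no order relative to randomisation.
- Section 10.4: a baseline heading, which shows intent but sets no time.
- Section 10.5: a data category and three completion modes, with no time for Day 1.
- Section 10.2: eligibility and consent must precede randomisation; the questionnaire is not mentioned.

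No passage sets the order.

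**Step 2: can allocation-related news arrive on Day 1?** Allocation is open (10.2). Results can be available in under one hour (4.1). The inclusion criteria assume that the result can be awaited for at most 4 hours before the decision (8.2). Arm, result and disposition can thus all be known within Day 1, and a site that completes the form afterwards on the same day has followed the plan.

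**Step 3: what would a late form do?** Let *e* be the difference between arms in mean Day-1 score that is caused by allocation alone. With change defined as follow-up minus Day 1:
- unadjusted change score: bias = −*e*;
- follow-up score adjusted for Day 1 with slope *b*: bias = −*b* × *e*. For an assumed *b* of 0.3 to 0.7 and *e* = 0.03, this is −0.009 to −0.021;
- direct comparison of Day-14 or Day-30 scores: no bias from this source.

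If only a share *f* of forms in one arm is late and each moves by *d*, then *e* = *f* × *d*. For example, one third of forms moving by 0.03 gives *e* = 0.01.

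**Step 4: illustration only.** Assumptions not in the documents: SD of change 0.20 to 0.30, *e* from 0.01 to 0.03, no true effect, and an unadjusted two-sided 5% test. From the plan: 1600/2 = 800 per arm. SE = SD × √(2/800) = SD × 0.05. Rejection probability = 1 − Φ(1.96 − *e*/SE) + Φ(−1.96 − *e*/SE).

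| SD | SE | *e* = 0.01 | *e* = 0.02 | *e* = 0.03 |
|---|---|---|---|---|
| 0.20 | 0.0100 | 17% | 52% | 85% |
| 0.25 | 0.0125 | 13% | 36% | 67% |
| 0.30 | 0.0150 | 10% | 27% | 52% |

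The table shows that at 800 per arm a small shift in the baseline mean matters. It does not estimate the shift in this trial.

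**The case against.** The strongest reply is that the protocol plainly intends a pre-intervention baseline and that several signs of late completion are weaker than they look. Much of this stands.

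- A reader might infer that the Enrollment column means after randomisation. It does not: patients can be enrolled while exclusion criteria 7-9 are still unknown (10.1), and section 13.1 speaks of patients enrolled but not randomised.
- A reader might infer that the emailed link is the Day-1 default, so that most baselines are answered after the patient leaves the ER. Section 10.5 sends patients seen face to face to paper, and Table 1 puts its online-questionnaire heading over Day 14 and Day 30 only.
- A reader might infer from 10.4, which names randomisation before the baseline list, that randomisation comes first. The same line names randomisation before the consent form, contrary to 10.2, so the list is not in time order.
- The remark in 7.1 that lack of blinding calls for objective outcomes is made about the primary endpoints. It applies here only by analogy.
- The eCRF completion guidelines cited in 10.5 are not among the documents and may set a time.

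What survives is narrower. These passages show intent and permit early completion, but none requires it. Section 10.5 makes no exception for Day 1 when it names the link, and paper completion has no ordering rule either. With up to 10 sites, practice can vary within the plan.

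**Conclusion.** The gap is real and worth closing. The sole baseline for a secondary endpoint may be recorded after allocation is known, in an open-label trial, without any breach of the protocol. The documents show that this can happen, not that it usually will.

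The size is unknown. The rejection rates above must not be read as the trial's error rate: they rest on an assumed SD, an assumed average shift between whole arms, and an unadjusted test that the plan never specifies. Baseline adjustment would reduce the bias without removing it. Treating Day 1 as the baseline is itself inferred from the endpoint wording and the baseline heading in 10.4, since section 13.4 gives no EQ-5D model. The consequences are confined to quality-of-life change and the economic inputs that draw on it.

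**What to change.** 1. In Table 1, mark the Day-1 EQ-5D-5L in the Screening (pre-randomisation) column.
2. In 10.4 and 10.5, state that it is completed on site, by paper, interviewer or tablet, after consent and before randomisation, with the completion time stored in the eCRF. Keep the emailed link for follow-up.
3. In the analysis plan, flag Day-1 forms completed after randomisation and pre-specify a sensitivity analysis that does not use them as baseline, for example a direct comparison of arms on the Day-14 and Day-30 scores. Do not simply set all late forms to missing: if sicker patients answer later, that would make the missingness selective.

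The cost is one table cell, a few sentences and one timestamp. The 5-10 minutes that section 10.5 allows for the questionnaire move ahead of randomisation, and some patients too unwell to answer will have no baseline.
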